- Prostvac (Prostvac™; developed by the National Cancer Institute [NCI] and licensed to BN Immunotherapeutics, Mountain View, CA) is a novel candidate prostate cancer immunotherapy for the treatment of prostate cancer. It is a viral vector based therapeutic cancer vaccine that is administered via subcutaneous injections. In a randomized controlled Phase 2 trial, Prostvac therapy was associated with a prolongation of survival in men with metastatic castrate-resistant prostate cancer. A phase III trial recently completed accrual of patients in this same population.
- There is also rationale to use therapeutic cancer vaccines such as Prostvac in earlier stage prostate cancer patients to maximize the potential therapeutic effect of immune stimulating therapy.
- Analysis of previous trials using therapeutic cancer vaccines alone suggests that such therapies may alter tumor growth rate.

Objective

Primary Objective:

- Determine if the therapeutic cancer vaccine prostvac can decrease tumor growth rate as measured by PSA rise after 6 months compared to a group getting surveillance alone.

[figure not shown]
Key Eligibility Criteria

- Histologically confirmed adenocarcinoma of the prostate
- Patients with negative CT Scan and Tc-99m Bone Scan
- Patients with a PSA over 0.8 ng/ml for patients following radical prostatectomy or for patients following definitive radiation therapy: a rise in PSA of ≥ 2 ng/mL above the nadir
- Patients with a PSA doubling time of 5-15 months
- No history of active autoimmune disease or history of organ compromising autoimmune disease
- ECOG 0-1

Design

- Randomized study
- Accrual goal is 36 evaluable patients per arm; randomized 1:1 to:
 - Arm A: Prostvac for 6 months with an additional optional year of maintenance for eligible patients OR
 - Arm B: Surveillance for 6 months, then Prostvac for 6 months with an additional year of maintenance for eligible patients

SCHEMA

- Prostvac Schedule: q 2 weeks for 1 month, then monthly for 5 months
- Eligible patients (with a doubling time >5 months will be able to continue vaccine maintenance for up to 1 additional year of vaccine)

TABLE OF CONTENTS

PRÉCIS	3
1 INTRODUCTION	9
1.1 Study Objectives	9
1.1.1 Primary Objective	9
1.1.2 Secondary Objectives.....	9
1.1.3 Exploratory Endpoints	9
1.2 Background and Rationale	9
1.2.1 Rationale for conducting the study in biochemically recurrent prostate cancer patients	9
1.2.2 Therapeutic Cancer Vaccines in Prostate Cancer	10
1.2.3 Prostvac	10

1 INTRODUCTION

1.1 STUDY OBJECTIVES

1.1.1 Primary Objective

- Determine if prostvac can decrease tumor growth rate as measured by PSA rise after 6 months compared to a group on surveillance for 6 months.

1.1.2 Secondary Objectives

- Observe the effects of vaccine on PSA growth rate when prostvac is initiated after 6 months of surveillance
- Evaluate immune response including phenotypic and functional marker analysis, CD4 cells, CD 8 cells, PSA-specific T-cells measured by response to PSA peptides in CD4 and CD8 lymphocytes, natural killer cells, Regulatory T-cells, Regulatory T-cell function, cytokines, and naïve thymic emigrants.
- Associate immunologic outcomes with PSA responses/changes in growth rates.

1.1.3 Exploratory Endpoints

Beginning with amendment G, patients enrolled onto either the immediate vaccine arm or the surveillance followed by vaccine arm will be asked to complete a prostate cancer specific QOL survey with 18 questions (MAX-PC) as well as the FACT-P survey. Associations will be made between survey responses and changes in PSA kinetics.

1.2 BACKGROUND AND RATIONALE

1.2.1 Rationale for conducting the study in biochemically recurrent prostate cancer patients

Prostate cancer is the most common malignancy among men in the United States with an estimated 220,800 new diagnoses and over 27,540 deaths in 2015.³ Although surgery or radiation can cure the majority of newly diagnosed patients, 20-40% are likely to have recurrent disease manifested as a rising PSA despite negative conventional imaging studies (CT and technetium-99m (Tc-99m) Bone Scan) used to detect metastasis.^{4,5} This stage of disease is often referred to as biochemically recurrent prostate cancer.

Despite the fact that nearly 90,000 men who are diagnosed each year with prostate cancer will ultimately develop biochemically recurrent prostate cancer there is no clear standard of care for these patients.⁶ Treatments range from active surveillance to intermittent or continuous androgen deprivation therapy (ADT) and in some cases salvage radiation or surgery. Ideal effective non-hormonal treatment strategies in this population would avoid or delay the onset of metastatic castration resistant prostate cancer (mCRPC). There are two significant obstacles to developing therapies in this asymptomatic population; (1) therapies need to have minimal toxicity (2) conventional clinical endpoints (metastatic progression and overall survival) can take 5-10 years.

1.2.2 Therapeutic Cancer Vaccines in Prostate Cancer

The goal of therapeutic cancer vaccines is to generate a targeted immune response leading to immune-mediated anti-tumor activity. Sipuleucel-T is a therapeutic cancer vaccine generated from peripheral blood mononuclear cells obtained from individual patients via leukapheresis. This vaccine is generated after a patient's peripheral immune cells are collected via leukapheresis, transported to a regional processing center where they are exposed in vitro to a PAP/GM-CSF fusion protein. At the end of this process, the activated cellular product is re-infused into the patient. A full course of therapy repeats this process 3 times every 2 weeks for 1 month.^{7,8} A phase III trial (n = 512) demonstrated an overall survival benefit for the vaccine (25.8 months vs. 21.7 months; P = 0.032).⁷ Based on these overall survival findings, the FDA approved sipuleucel-T for the treatment of asymptomatic or minimally symptomatic mCRPC, making it the first FDA-approved therapeutic cancer vaccine for the treatment of any malignancy.

1.2.3 Prostvac

Prostvac (Prostvac™; developed by the National Cancer Institute [NCI] and licensed to BN Immunotherapeutics, Mountain View, CA), offers an alternative strategy to sipuleucel-T.^{2,9} (The LTIB and BN Immunotherapeutics have an ongoing CRADA for the preclinical and clinical development of Prostvac.) To target prostate-specific antigen (PSA), Prostvac vaccine employs genetically altered poxviruses to deliver targeting information to immune cells and generate an immune response. Administered subcutaneously, the poxviruses deliver the transgenes for the tumor associated antigens (PSA) to antigen presenting cells through cellular infection. Once these pox viruses are within the cellular cytoplasm, the transgenes are processed. The end result is an antigen presenting cell expressing a PSA peptide within the major histocompatibility complex, resulting in PSA-specific cytolytic T lymphocytes activation.^{10,11} (Figure 2) This approach does not require expensive, labor-intensive *ex vivo* preparation of patients' peripheral blood. Prostvac is thus potentially more logically and financially feasible over the long-term than sipuleucel-T¹².

Prostvac has been investigated in 2 phase II trials in mCRPC, both of which administered the vaccine at monthly intervals until disease progression. An industry-sponsored, placebo-controlled, multicenter trial in 125 mCRPC patients randomized them 2:1 in favor of Prostvac; the placebo was an empty poxviral vector containing no transgenes. As was seen in the sipuleucel-T studies, patients receiving vaccine showed no change in short term disease progression, yet had an overall survival benefit (25.1 months with Prostvac vs. 16.6 months with placebo; P = 0.0061).¹ (Figure 1) A second phase II study of Prostvac in 32 mCRPC patients at the NCI demonstrated that the vaccine was able to generate a T-cell specific immune response¹³. Based on the findings in these trials, a phase III trial of Prostvac in mCRPC is currently underway⁽¹¹⁾.

[figure not shown]

Figure 2: Poxviral vaccine strategy: Modified poxvirus contains transgenes for the tumor-associated antigen PSA and 3 T-cell costimulatory molecules.²

Figure 1: Prostvac improved survival in mCRPC patients in a randomized multi center phase II.¹

Prostvac is very well-tolerated, with common side effects of grade 1 injection-site reactions or flu-like symptoms.^{1,13} A favorable side effect profile and the potential ability to induce a sustained antitumor immune response, clinical trials are ongoing evaluating strategies to use Prostvac in earlier disease patients.

A phase III trial (NCT01322490) of Prostvac monotherapy, however, was reported to have not met its primary endpoint of overall survival in September, 2017. Nonetheless, the rationale for use of Prostvac in earlier stage prostate cancer remains scientifically rational and this trial will continue. Furthermore, at this point neither this trial nor the phase III trial have suggested a safety concern for Prostvac.

1.2.4 The Importance of Evaluating the Immunologic Response

Our group in the LTIB has previously evaluated immunologic parameters in clinical trials with Prostvac among several immunotherapy studies.^{13,14} While these findings are not surrogate markers of response, they have improved our knowledge of a vaccine-generated immune response and provided a better understanding of what factors are potentially important in mounting a sufficient anti-tumor immune response that could be associated with improved clinical outcomes. These and other data may allow optimization of vaccines in subsequent clinical trials. Few groups are as well positioned and have the experience as the LTIB to conduct this rigorous immune testing from clinical samples of patients treated with Prostvac.

PSA-Specific Immune Responses. While many clinical trials have been done in biochemically recurrent prostate cancer, there is little reported on the impact of those therapies on the immunologic response that is near the depth and scope that is proposed in this trial. The proposed immunologic studies will be done on all patients by the Laboratory of Tumor Immunology and Biology at the NCI Clinical Center under the direction of [name].

Unlike previous studies involving Prostvac, which evaluated immune responses to a single 9 amino acid section of the 244 amino acid PSA protein, the immune analysis in this trial will

evaluate overlapping 15 amino acid sequences of the entire PSA protein. (Figure 3). This more extensive analysis will provide a more thorough understanding of the immune response initiated by Prostvac and a greater opportunity for clinical correlations. This type of analysis has not been previously prospectively performed in biochemically recurrent prostate cancer patients. Advantages of this approach include the ability to assess both CD4 and CD8 T cells, identification of multifunctional T cells (those producing ≥ 2 cytokines), and identification of T lymphocytes with lytic potential (CD107a expression). (Table 1).

[figure not shown]

Figure 3: Overlapping PSA Peptide Assessment. This innovative approach to evaluating immune response allows for assessment of immune response to the entire PSA protein using overlapping 15 amino acid sequences. (Previous techniques have focused on assessing just one of these peptides.)

PT	Immune Responses to PSA							
	CD4				CD8			
	CD107a	IFNg	IL2	TNF	CD107a	IFNg	IL2	TNF
Cohort 1 – No Vaccine	11							
	13							
	20							

Briefly, the methodology takes cryopreserved peripheral blood mononuclear cells (PBMCs) from patients before therapy and at the time of restaging. They are thawed and rested overnight at 37°C, 5% CO₂ in complete media (IMDM supplemented with 10% Human AB, 2mM glutamine, 100 units/ml penicillin, and 100 µg/ml streptomycin). The next day (Day 0), PBMCs are seeded in 12 well plates (2.5×10^6 in 1 mL), and stimulated with peptide mixes (0.1µg/mL per peptide); cultures were supplemented on days 3 and 5 with cytokines (IL7 and IL15, 10 ng/mL, PeproTech, Rocky Hill, NJ) and fresh media, and on day 7 are rested (with removal of cytokine and peptide). On day 11, 1×10^6 cells were restimulated for 24 hours in 96 well plates with peptide mixes in the presence of anti-CD107a-APC (clone H4A3, BD Biosciences); brefeldin A (1ul/mL) and monensin (0.7ul/mL) (BD Biosciences) are added to cultures 2 hours after the start of the restimulation and incubated for the final 22 hours. PBMCs are then stained with anti-CD4-PerCP-Cy5.5 (clone OKT4, Biolegend), anti-CD8-AF700 (clone OKT8, Ebioscience), and anti-TNF-PE (clone MAAb11), anti-IFN γ -PE-Cy7 (clone 4SB3), and anti-IL-2-BV521 (clone 5344.111) (BD Biosciences). At least 3×10^5 events in the live gate are acquired with a BD LSR-II flow cytometer equipped with a UV, violet, blue, and red laser. FCS files are analyzed with FlowJo V.9.7 for Macintosh (TreeStar, Ashland, OR). Fluorescence minus one (FMO) controls are used for gating, and non-viable cells were excluded. The absolute number of CD4 $^+$ or CD8 $^+$ lymphocytes producing cytokine or positive for CD107a is calculated per 1×10^6 cells plated at the start of the IVS. The background signal (obtained with the HLA peptide pool), and values obtained prior to therapy were subtracted from those obtained post-therapy. Values ≥ 250 are scored as positive for TAA-specific immune response following therapy. ([Figure 4](#))

[figure not shown]

Figure 4: Methodology of Assessing PSA-specific Immune Responses

Flow Cytometry Analysis of Immune subsets (Biomarker Development)

As part of the extensive immune interrogation, peripheral immune cells will be evaluated by 30 markers to assess 127 immune subsets. ([Table 2](#)) This methodology has been previously described.¹⁵ This added analysis will provide preliminary data to develop a Peripheral Immunoscore based on the frequency of specific pre-determined immune cell subsets in the

blood of patients prior to therapy. The score is calculated from the frequency of certain immune cell subsets prior to vaccine treatment. The panel of markers will also be used to measure immune response to the vaccine. The ultimate goal is to use this Peripheral Immunoscore as a biomarker that could serve as an intermediate marker of immune response in future studies. Data from this study would be used to establish the relevant markers and can be confirmed in future studies. The first step has been performed in a previous study with another pox viral vaccine in breast cancer (unpublished data; **Figure 5**)

[figure not shown]

Figure 5: Preliminary Data of Immunoscore Associations with Clinical Outcomes. This data (unpublished) from a recently completed breast cancer study involving a therapeutic cancer vaccine highlights the potential of Immunoscore. In this study, patients with peripheral immunoscore (H, more than 13 parameters positive, measured prior to therapy) had a significant increase in progression free survival. This difference was only observed in the vaccine arm and not in the standard of care alone arm. A separate assessment is required in prostate cancer and will be done in this study. If similar findings are seen, the Immunoscore could be prospectively evaluated in future trials using the data from this study to establish which immune subsets are most relevant.

Table 2: Analysis of Peripheral Immune Cells

1. **CD4:** Helper T lymphocytes (32 subsets)
2. **CD8:** Cytotoxic T lymphocytes (29 subsets)
 - **Markers of PD-1 pathway and T cell activation (in CD4 and CD8):**
 - EOMES: activation
 - TCR- $\alpha\beta$: activation
 - Tbet: activation
 - BATF: activation/exhaustion
 - **Maturation status of T lymphocytes (in CD4 and CD8):**
 - **Naïve:** CD45RA $^{+}$ CCR7 $^{+}$
 - **Effector Memory:** CD45RA $^{-}$ CCR7 $^{+}$
 - **Terminal (EMRA):** CD45RA $^{+}$ CCR7 $^{-}$
 - **T lymphocyte markers (in CD4 and CD8):**
 - CTLA-4: inhibition
 - PD-1: activation/inhibition
 - PD-L1: activation/cross-inhibition
 - TIM-3: inhibition
 - ICOS: activation (only on CD4)
3. **Tregs:** Regulatory T lymphocytes (CD4 $^{+}$ CD25 $^{+}$ FoxP3 $^{+}$ CD127 $^{-}$) (7 subsets)
 - **CD45RA:** Tregs highly expandable *in vitro*
 - **CTLA-4:** Treg suppression
 - **CD49d:** “contaminating” effector lymphocytes (non-Tregs)
 - **ICOS:** Treg suppression
 - **PD-1:** activation/inhibition
 - **PD-L1:** cross-inhibition
4. **B lymphocytes:** CD19 $^{+}$ (5 subsets)
 - **CTLA-4:** inhibition
 - **TIM-3:** inhibition
 - **PD-1:** activation/inhibition
 - **PD-L1:** cross-inhibition
5. **NK:** Natural killer cells (CD56 $^{+}$ CD3 $^{-}$) (20 subsets)
 - **CD16 $^{+}$ CD56 br :** Functional intermediate, lytic and cytokine production
 - **CD16 $^{+}$ CD56 dim :** Mature NK, cytokine production
 - **CD16 $^{+}$ CD56 br :** Immature, abundant in human placenta

- **CD16** **CD56^{dim}**: non-lytic, non-cytokine production
- **TIM-3**: activation
- **PD-1**: activation/inhibition
- **PD-L1**: cross-inhibition

6. **NK-T**: CD56⁺ CD3⁺ (4 subsets)
• **TIM-3**: activation
• **PD-1**: activation/inhibition
• **PD-L1**: cross-inhibition

7. **cDCs (Conventional DCs)**: CD3⁻CD56⁻CD1c⁺CD303⁻
(5 subsets)

8. **pDCs (plasmacytoid DCs)**: CD3⁻CD56⁻CD1c⁻CD303⁺
(5 subsets)
• **Markers of DC activation**

- **CD83**: activation
- **TIM-3**: inhibition
- **PD-1**: activation/inhibition
- **PD-L1**: cross-inhibition

9. **MDSCs**: Myeloid-derived suppressor cells (CD11b⁺
HLA-DR^{low/-} CD33⁺) (20 subsets)
• **CD14**: Common Myeloid Marker (high in monocytes, dim in granulocytes)
• **CD15**: Granulocyte marker
• **CD16**: most immature monocytic MDSCs
• **PD-1**: activation/inhibition
• **PD-L1**: cross-inhibition

1.2.5 Rationale for Changes in Growth Rate as Primary Endpoint

Monotherapy with a therapeutic cancer vaccine or immune check point inhibitor has previously demonstrated improved survival without short-term changes in progression.^{3,9,14,15} Therefore, short term clinical end points are unlikely to determine the clinical potential of vaccines in patients with prostate cancer, especially given the anticipated heterogeneity of the population and likelihood for prolonged survival after enrollment. A previous analysis of prostate cancer clinical trials at the NCI suggested that a therapeutic cancer vaccine may alter the tumor growth rate after treatment, thereby having no effects on delaying short-term progression yet improving long term outcome. This data suggested that the decreased growth rate of the tumor continued even after the vaccine was discontinued; perhaps suggesting a sustained vaccine-initiated immune response impacted the tumor growth rate. This is contrasted with cytotoxic chemotherapy which led to initial reductions in tumor size, but then growth rate resumed at the same pre-treatment rate once cytotoxic therapy was discontinued.¹⁶ (Figure 6) Furthermore, unpublished data from an ECOG trial in non-metastatic prostate cancer demonstrates that a reduced growth rate was seen after treatment with a vaccine and was demonstrable within 100 days of vaccine initiation. (Figure 7). Together, these data suggest that vaccines may be able to impact tumor growth rates thereby potentially improving survival, and such changes can be seen as early as 3 months after initiating therapy.

The prospective use of tumor growth rate changes after treatment with a vaccine may introduce a new perspective and method in the assessment of therapeutic cancer vaccines and check point inhibitors. Given the indolent nature of biochemically recurrent prostate cancer, a 50% reduction in the growth rate could have substantial implications on survival.^{16,17}

Vaccines May Impact Tumor Growth Rate and Thereby Impact Survival

[figure not shown]

Figure 6: Retrospective data suggests that therapeutic cancer vaccines can alter the growth rate of tumors over time leading to an impact on overall survival.

1.2.6 Rationale for Using a 6-Month Endpoint to Evaluate Change in the Growth Rate

An analysis of the ECOG trial 9802, which treated castration-sensitive non-metastatic prostate cancer patients (n=29) suggests a vaccine targeting PSA alters tumor growth rate, as measured by PSA ($\log g$ (growth rate) \pm SE (standard error)), within 80 to 100 days (Figure 7).¹⁸ This retrospective analysis used the tumor growth rate equation determined that by day 80 after Prostvac therapy was initiated a statistically significant change in tumor growth rate was detectable compared to baseline.¹⁶ This altered growth rate was sustained at day 100 as well. These data support the hypothesis that vaccines exert their therapeutic effect not by reducing tumor burden, but by altering tumor growth rate. (The current study differs E9802 in that it is randomized to immediate or delayed vaccine with a primary focus on the immune impact of the vaccine on tumor growth rates.)

[figure not shown]

Figure 7: Prostvac can affect growth rate in 80 days. An analysis of the ECOG trial 9802, which treated castration-sensitive non-metastatic prostate cancer patients (n=29) suggests Prostvac alters tumor growth rate, as measured by PSA ($\log g$ (growth rate) \pm SE (standard error)), within 80 to 100 days. This retrospective analysis used the tumor growth rate equation determined that by day 80 after Prostvac therapy was initiated a statistically significant change in tumor growth rate was detectable compared to baseline. This altered growth rate was sustained at day 100 as well. These data support the hypothesis that vaccines exert their therapeutic effect not by reducing tumor burden, but by altering tumor growth rate.

This trial will provide an opportunity to prospectively define the mechanism by which vaccines can impact tumor growth rate.

1.2.7 Tumor Growth Kinetics

The regression-growth equation

Drs. Stein and Fojo at the NCI have developed an equation based on the assumption that the change of a tumor's quantity during therapy results from 2 independent component processes: an exponential (first-order kinetics) decrease/regression and an exponential regrowth of the tumor¹⁹. The equation is $f(t) = \exp(-d * t) + \exp(g * t) - 1$ (A) where \exp is the base of the natural logarithm, $e = 2.7182$, and $f(t)$ is the tumor (or in MTC calcitonin) measurement at time t in days, normalized to (divided by) the tumor measurement at day 0, the time at which treatment is commenced. Rate constant d (decay, in days⁻¹) represents the exponential decrease/regression of

the serum tumor marker (i.e. PSA) signal during therapy. Rate constant g (growth, also in days⁻¹) represents the exponential growth/regrowth of the tumor during treatment. These rate constants may be expressed in terms of half-lives and doubling times. Thus, d equals \ln_2 (0.693) divided by the time it takes for the regressing part to shrink by half, whereas g equals \ln_2 divided by the time for the growing component to double.¹⁶

Two earlier papers depict theoretical curves depicting the separate components of Equation (A) and how these combine together to give the time dependence of the tumor size, f (18,19). When the data showed a continuous decrease from the time of treatment start, so that only the regression parameter d was found to differ significantly from zero with $P < 0.05$, Equation (A) was replaced by the following reduced form, with the growth rate constant eliminated: $f(t) = \exp(-d * t)$ (B) When tumor measurements showed a continuous increase, so that only the growth parameter g was found to differ significantly from zero with $P < 0.05$, Equation (A) was replaced by the following reduced form, with the decay constant eliminated: $f(t) = \exp(g * t)$.^{19,20}

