2.3.2 Treatment Assignment and Randomization Procedures

Cohorts

Number	Name	Description
1	Prostate Cancer	Male patients diagnosed with prostate cancer (non-metastatic), with demonstrated biochemical progression, a PSA doubling time of 5-15 months, and with a rising PSA.

Arms

Letter	Name	Description
A	PROSTVAC treatment	PROSTVAC treatment for 6 months with an additional optional year of maintenance for eligible patients
B	Delayed PROSTVAC treatment	Surveillance for 6 month followed by PROSTVAC treatment for 6 months with an additional year of maintenance for eligible patients

Randomization and Arm Assignment

Subjects in Cohort 1 will be randomized on a 1:1 basis to **Arm A** or to **Arm B**. The computerized randomization will be performed by the NCI Central Registration Office. CRO staff will send a secured e-mail with the Verification of Registration of the patient and treatment arm patient is randomized to. This process will be completed within 15–30 minutes of sending the eligibility checklist. CRO will keep track of all randomization data in Clinical Data Registry (CDR) of CRO.

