8 STATISTICAL CONSIDERATIONS

The primary endpoint of this trial is to determine if prostvac can slow the growth rate of prostate cancer relative to a group of patients on surveillance. With 36 evaluable patients with a growth rate value from 0 to 6 months on the Prostvac arm and 36 evaluable patients on the surveillance arm (72 total patients) there would be adequate patients to have 80% power to test for a difference between the two arms of a change in growth rate from baseline equal to 2/3 SD of the change (0.67 SD effect size) using a 0.05 significance level two-tailed two group t-test. In practice, if the distributions of the growth rate constants are not normally distributed ($p < 0.05$ by a Shapiro-Wilks test), then a Wilcoxon rank sum test may be used instead of a two-sample t-test. In order to allow for a small number of inevaluable subjects as well as to accommodate screen failures, the accrual ceiling will be set at 110. (It is estimated that it will take 4 years to complete accrual to this trial.)

Secondary Endpoints

In addition, using the surveillance arm, two related endpoints will be explored, both the actual magnitude of the change in the growth rate parameter as well as the fraction who exhibit a substantial, 50% decline in the growth rate as a result of treatment. For the 36 patients who will be enrolled on the surveillance arm, the growth rate determined at 12 months (after 6 months of vaccine) will be subtracted from that obtained at 6 months (after surveillance) to determine the actual change in the growth rate for receiving vaccine after 6 months of surveillance. With 36 patients, there is 83% power to detect a difference in the values at the two time points equal to 1/2 of the SD of the change (.50 effect size) assuming that a two tailed 0.05 alpha level paired t-test is used.

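### The growth-rate fit is pinned to the single day-0 PSA, which costs efficiency relative to a fit with its own starting level; the stated 80% power and the validity of the randomised test are unaffected.

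*Combined protocol and SAP*

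**What the plan says.** Section 1.2.7 defines f(t) as the measurement "normalized to (divided by) the tumor measurement at day 0, the time at which treatment is commenced". Equation (A) is f(t) = exp(−d·t) + exp(g·t) − 1. The reduced forms are exp(−d·t) for a continuous fall and exp(g·t) for a continuous rise. Section 1.2.7.1 fits this to each patient and mentions neither a fitted starting level nor an averaged baseline.

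Section 8 requires "36 evaluable patients with a growth rate value from 0 to 6 months on the Prostvac arm", with the same number on surveillance. It claims "80% power to test for a difference between the two arms of a change in growth rate from baseline" of 0.67 SD, "using a 0.05 significance level two-tailed two group t-test". It refers to growth rate constants without naming an estimator, and Section 1.2.7 defines the only one.

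On timing, Section 1.2.6 reports from an earlier 29-patient trial, analysed with this equation, that "by day 80 after Prostvac therapy was initiated a statistically significant change in tumor growth rate was detectable compared to baseline".

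**The concern.** At t = 0 Equation (A) gives 1 + 1 − 1 = 1, and both reduced forms give 1, whatever d and g are. The day-0 PSA is thus treated as free of error. Any error in it moves every later ratio in the same direction, and the fitted rate absorbs it.

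A slope forced through the first point also gives the early visits more influence than a slope with its own intercept does. If the vaccine takes time to act, the pinned rate records less of the slowing.

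At stake is the precision of the primary endpoint. The scheduled PSAs could support a less noisy growth rate, and so more power for the same 72 men.

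**Working it through.** **The plan's own figure.** Inputs from Section 8: 36 per arm, 0.67 SD, two-sided 0.05 t-test. Noncentrality = 0.67 × √(36/2) = 2.84 on 70 df, giving power of 80.1% (79.7% at exactly 2/3 SD). The stated 80% reproduces.

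**Error variance of the slope.** Visits are from Appendix C. Let y = ln(PSA_t/PSA_0) = g·t + e_t − e_0, with independent errors of variance s².

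- Pinned slope Σty/Σt²: variance s²[1/Σt² + (Σt)²/(Σt²)²]. The second term is the day-0 error.
- Slope with its own intercept: variance s²/Σ(t − t̄)².

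Arm A, days 0, 14, 28, 56, 84, 112, 140, 168: Σt = 602, Σt² = 71,540, Σ(t − t̄)² = 26,239.5.
- Pinned: 1/71,540 + 602²/71,540² = 8.48 × 10⁻⁵ s²
- Free: 1/26,239.5 = 3.81 × 10⁻⁵ s²
- Ratio 2.22

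Arm B, months 0 to 6: Σt = 21, Σt² = 91, Σ(t − t̄)² = 28.
- Pinned: 1/91 + 441/8,281 = 0.0642 s²
- Free: 1/28 = 0.0357 s²
- Ratio 1.80; the day-0 value supplies 0.0533/0.0642 = 83% of the pinned variance

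If errors instead accumulate as a random walk, the Arm B variances are 0.187 (pinned) and 0.179 (free) per unit of monthly step variance, so the advantage almost disappears.

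**Share of a delayed slowing that is captured.** Let the slowing begin at day L and u = max(t − L, 0). The pinned share is Σtu/Σt²; the free share is Σ(t − t̄)u/Σ(t − t̄)². On Arm A visits (t̄ = 75.25):
- L = 60: 37,184/71,540 = 52% pinned; (37,184 − 75.25 × 264)/26,239.5 = 66% free
- L = 80: 27,104/71,540 = 38% pinned; (27,104 − 75.25 × 184)/26,239.5 = 51% free

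**Power at 36 per arm.** Assumptions: doubling time uniform over the eligible 5–15 months (Section 2.1.1.4 gives the range, not the shape); true slowing of 50%; baseline-rate error SD 0.001/day; PSA CV 10% with independent errors. The pinned exponential least-squares fit and the ln(PSA) slope with intercept were simulated on the scheduled visits, and power was taken from the noncentral t on 70 df.

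| Slowing starts | Pinned | Free level |
|---|---|---|
| Day 0 | 97% | 99% |
| Day 14 | 94% | 99% |
| Day 28 | 87% | 97% |
| Day 60 | 58% | 83% |
| Day 80 | 36% | 60% |

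At CV 5% the figures are about 72% v 89% (day 60) and 49% v 71% (day 80).

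**A second calibration, with no delay.** Suppose 0.67 SD describes a free-level fit and PSA noise makes up 10%, 25% or 50% of the variance of the change. Using the Arm B ratio, pinning multiplies that variance by 1 + 0.8 × share = 1.08, 1.20 or 1.40. Power falls from 80% to 77%, 73% or 66%.

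**The case against.** The strongest reply is that nothing in the sample-size statement is wrong, and that stands. The effect is expressed in SDs of the measured change, so estimator noise is already inside the unit. A reader might infer that the trial has less than its stated power; the documents do not support this. Pinning changes only how large a raw slowing 0.67 SD represents. A reader might also infer bias in the primary comparison, but random day-0 error is balanced in expectation by randomisation.

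The second reply is that late onset is not what Section 1.2.6 says, and this also stands. Detectable by day 80 is not onset at day 80. Take the assumptions above, CV 5–10%, 29 men, a pinned log fit and assumed draws at days 0, 14, 28, 56 and 80. The chance of a significant change by day 80 is then about 2–3% for onset at day 80, 7–10% at day 60, 35–70% at day 28 and 83–99% at day 0. The earlier trial thus points to early onset, where pinned power stays above 80% in the table. The day-60 and day-80 rows are scenarios only.

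Third, a bare ln(PSA) slope measures net change and discards the decay constant d, which misstates g in men whose PSA falls and then regrows. That is right, and the fix must keep d for them.

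Finally, a free level should not be credited with too much. It cures dilution only in part: 34% of the slowing is still missed at day-60 onset and 49% at day 80. Nor does it remove the shared error at Arm B's C1D1 PSA, which still ends the surveillance window and starts the vaccine window. The simulated error correlation between the two rates is −0.28 pinned and −0.26 free.

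**Conclusion.** The concern holds as one of efficiency. The only defined growth-rate estimator treats one PSA as exact. With independent errors on log PSA, its error variance is about twice what the same draws allow, and it captures less of any delayed slowing.

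The cost in power ranges from negligible to large, and the documents do not settle where it lies. They give no PSA measurement error, raw SD of the change or onset delay. At an assumed CV of 10% the gap is about 2 points with immediate onset, 10 points at day 28 and 24–25 points at days 60–80. Under the second calibration with no delay it runs from 0 (no PSA noise) to about 14 points (noise half the variance). The variance advantage almost vanishes if PSA errors drift as a random walk. In no scenario examined did pinning give more power.

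The plan's 80%, its test and its sample size need no correction on this ground.

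**What to change.** In Sections 1.2.7.1 and 8, name the estimator and give it a fitted starting level, so that the day-0 PSA is one observation among the others:

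- For a continuously rising PSA: the slope of ln(PSA) on actual draw dates, with a patient-specific intercept. Actual dates matter because Appendix C lets Arm A use a screening PSA up to 16 days old as the C1D1 value.
- Where the decay term is significant: Equation (A) with a free starting multiplier, so that d and g are both kept.
- The same rule in both arms for the 0–6-month window, and in Arm B's vaccine window. State which visit is day 0 for surveillance, since Section 1.2.7 ties day 0 to the start of treatment.
- The published day-0-normalised constant as a sensitivity analysis.

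This costs protocol and SAP wording only, with no new visits or samples. The downside is that the primary constant is no longer identical to that of the earlier trials the rationale relies on; the sensitivity analysis preserves that comparison.
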